7.1.3. Temporary Discontinuation of Study Intervention

Infection-related criteria for temporary discontinuation of study intervention

This table describes the required criteria for temporarily discontinuing study intervention and the next steps the site staff should follow.

If a participant develops	Then follow this guidance
serious or opportunistic infections, as defined in the	Withhold study intervention until resolution of all
exclusion criteria (Section 5.2)	acute clinical signs and symptoms, and completion of
	all appropriate anti-infective treatment.
	The investigator should consult with the sponsor-
	designated medical monitor to determine when it is
	appropriate to restart study intervention.
any acute infection or illness	At the discretion of the investigator and sponsor or its
	designee, withhold intervention until resolution of all
	acute clinical signs and symptoms, and completion of
	all appropriate anti-infective treatment.
positive HBV DNA results	Contact the sponsor-designated medical monitor.
or	Repeat HBV DNA testing as soon as possible.
results detecting HBV DNA, but the HBV DNA is	If HBV DNA is confirmed as positive, then
below the level of quantification	permanently discontinue intervention.
LTBI and the participant is a candidate for LTBI	Withhold study intervention for at least the first 4
treatment	weeks of LTBI treatment.
	If there is no evidence of hepatotoxicity
	(ALT/AST must remain ≤2 times ULN) or other
	treatment intolerance after receiving at least 4
	weeks of appropriate LTBI therapy, per WHO or
	CDC guidelines, then restart study intervention.
	The participant must complete appropriate LTBI
	therapy before restarting study intervention.

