8.2.9. Hepatitis B Testing and Monitoring

The following actions should be taken in response to HBV DNA test results during the study.

If	Then
a single result is obtained with a value "below limit of	the test should be repeated within approximately
quantitation"	2 weeks
the repeat test result is "target not detected"	monitoring may resume according to the study
	schedule
the participant has 2 or more test results with a value	HBV DNA testing should be performed approximately
"below limit of quantitation" during the study	once per month for the remainder of the study and
	referral to a hepatologist is recommended
a result is obtained with a value "above limit of	the participant will be permanently discontinued from
quantitation" at any time during the study	the study intervention (see Section 7.1) and should be
	referred to a hepatologist immediately.

Management of enrolled participants with detectable HBV DNA during the study

If HBV DNA is detected, study intervention will be temporarily withheld or permanently discontinued, as described in Sections 7.1 and 7.1.3, and the participant should receive appropriate follow-up medical care.

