A listing of patients with detectable hepatitis B virus (HBV) DNA will be provided.

HBV DNA status (not detectable, detectable but not quantifiable [that is, <lower limit of detection (LLOD)], quantifiable [that is, ≥LLOD]) will be summarized, stratified by applicable baseline HBV serology status.

A summary table of herpes zoster will be provided, including event maximum severity, seriousness, whether resulting in temporary study drug interruption, whether resulting in study drug discontinuation, and event outcome. See Appendix 10 (Section 6.10) for PT list for herpes zoster.

A summary table of herpes simplex will be provided, including event maximum severity, seriousness, whether resulting in temporary study drug interruption, whether resulting in study drug discontinuation, and event outcome. See Appendix 10 (Section 6.10) for PT list for herpes simplex.

The time to onset of first treatment-emergent infectious AE during the Treatment Period will be defined as follows:

```
Time to onset of first treatment-emergent infectious AE (in weeks) = (Start\ date\ of\ first\ infectious\ AE - Date\ of\ first\ injection\ +1)/7.
```

Note that if an infectious AE was preexisting prior to the date of first injection and subsequently became treatment-emergent due to worsening post-baseline, the date of worsening will be used in place of the AE start date.

If a patient does not have a treatment-emergent infectious AE during the Treatment Period, they will be censored at the date of completion or ED from the Treatment Period. Kaplan-Meier estimates of the proportion of patients not yet experiencing their first treatment-emergent infectious AE at 12, 24, 36, 48, and 60 weeks will be provided for each treatment arm. A Kaplan-Meier plot of the time to onset will be presented by treatment arm.

The duration of each treatment-emergent infectious AE during the Treatment Period will be defined as follows:

```
Duration of treatment-emergent infectious AE (in weeks) = (End date of AE – Start date of AE + 1) / 7.
```

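### SAP 4.6.2.4 splits detectable HBV DNA results at the limit of detection, against its own category names and the protocol's limit-of-quantitation boundary

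*SAP*

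**What the plan says.** SAP 4.6.2.4 (Infections) plans two outputs on HBV DNA. One is a listing: "A listing of patients with detectable hepatitis B virus (HBV) DNA will be provided". The other is a summary of HBV DNA status, stratified by baseline HBV serology. It has a not-detectable class and two further classes, given as "detectable but not quantifiable [that is, <lower limit of detection (LLOD)], quantifiable [that is, ≥LLOD". The abbreviation is written out in full, so the term is not a text-extraction fault.

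The protocol describes the same kinds of result in two places.

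- Section 7.1.3, in the table of infection-related criteria, has an entry for "results detecting HBV DNA, but the HBV DNA is" and completes the phrase with "below the level of quantification".
- Section 8.2.9 uses three result categories. The negative one appears in the row where "the repeat test result is 'target not detected". The low-level one appears where "the participant has 2 or more test results with a value", completed by "below limit of quantitation' during the study". The high one appears where "a result is obtained with a value 'above limit of", and the limit named is again that of quantitation.

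SAP 4.9 declares no change from the protocol-planned analyses, so the SAP does not present its cut-off as a deliberate departure.

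**The concern.** The SAP's class names and its rule disagree. The names ask whether a detected result can be quantified. The rule asks whether it reaches the detection limit. On a plain reading, a result below that limit has not been detected, so the middle class is defined by a condition that belongs to the class beneath it. The protocol uses a different boundary for the same distinction.

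At stake is whether one safety table can be read correctly. Exclusion criterion 22 bars participants with current HBV infection, giving a positive HBV DNA result as an example. HBV DNA found on study is therefore of clinical interest, and infections are among the adverse events of special interest in SAP 4.6.2. A reader who compares the quantifiable count with the protocol's category above the limit of quantitation would expect the two to mean the same thing. Under the literal SAP rule they might not.

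**Working it through.** No sample size, power or error-rate figure is involved, and the plan states no figure to reproduce. The check maps each possible result through both sets of definitions.

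**Inputs**
- SAP cut-off: LLOD, expanded as lower limit of detection (SAP 4.6.2.4).
- Protocol cut-off: limit of quantitation (Protocol 7.1.3 and 8.2.9), written LLOQ below.
- Values of LLOD and LLOQ: not given. Assumption: LLOD ≤ LLOQ.
- Number of participants with HBV DNA results on study: not given.

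**Mapping of a result x on the literal text**

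| Result | SAP 4.6.2.4 | Protocol 8.2.9 | Agree? |
|---|---|---|---|
| Not detected | Not detectable by name, but also meets the <LLOD bracket of the middle class | Target not detected | Ambiguous in the SAP |
| Detected, LLOD ≤ x < LLOQ | Quantifiable, because x ≥ LLOD | Below limit of quantitation | No |
| x above LLOQ | Quantifiable | Above limit of quantitation | Yes |

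The second row is where the outcome depends on facts outside the documents:

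1. **LLOD < LLOQ, bracketed rule applied to numeric values.** Every result in the interval from LLOD up to, but not including, LLOQ is tabulated as quantifiable. The protocol calls the same result below the limit of quantitation.
2. **LLOD = LLOQ.** The interval is empty and no result moves.
3. **Classification by laboratory result code.** A result reported as below the limit of quantitation falls into the middle class by name. No result moves, whatever the two limits are.

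In cases 2 and 3 only the wording is wrong.

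**After replacing LLOD with LLOQ in both brackets.** The classes become target not detected; detected and x < LLOQ; x ≥ LLOQ. Each result meets exactly one condition, and the three classes line up with the categories in Protocol 8.2.9. The protocol rows speak of below and above the limit; a value exactly at the limit goes to the top class under the SAP's own ≥ convention.

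**The case against.** The strongest reply is that this is a slip of terminology. The three SAP names correspond one for one to the protocol's result categories, so the limit of quantitation was probably meant. Protocol 8.2.9 puts its result categories in quotation marks, as if they were reported codes. A result reported that way may carry no number to compare with an LLOD, and a programmer would naturally sort it by name. The listing of detectable HBV DNA does not depend on the cut-off and would show every such patient. Most of this stands, and it limits the consequence. It does not correct the rule: the SAP is the specification for the table, and the only explicit cut-off it gives is the wrong one. The version history shows that Section 4.6.2.4 was revised in Versions 2 and 3, and the current text still carries it.

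Three stronger readings are tempting, and the documents do not support them.

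- A reader might infer that all detected results below quantitation are misclassified. That requires case 1 above, and no document establishes it.
- A reader might infer that the middle class must be empty. Because it overlaps the not-detectable class, it could instead collect undetected samples, depending on the order in which the conditions are programmed. It could also hold signals reported as detected below the stated LLOD, if the assay reports any.
- A reader might infer that the table would overstate HBV reactivation. The SAP does not define reactivation from this table; it selects infectious events, including hepatitis reactivation, through the MedDRA system organ class for infections.

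Nor is quantitation the protocol's only line for action. Section 7.1.3 puts positive results and detected results below quantification in the same row. The mismatch shown here is therefore one of result categories.

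**Conclusion.** The definition in SAP 4.6.2.4 is wrong as written. It contradicts its own class names and differs from the boundary in Protocol 7.1.3 and 8.2.9. Whether any result would be tabulated in the wrong class is conditional: it requires an LLOD below the LLOQ and literal use of the bracketed rule. Under those conditions the shift goes one way, from below quantitation to quantifiable. Otherwise the fault is in the wording alone.

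The number of participants affected cannot be derived from the documents and may be zero. The reach is one descriptive safety summary. The by-patient listing, participant management and all efficacy analyses are unaffected. The point is worth correcting because it sits in an operative analysis rule and the correction is trivial.

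**What to change.** In SAP 4.6.2.4, replace LLOD with the lower limit of quantitation (LLOQ) in both brackets and name the classes:

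- target not detected;
- detected but <LLOQ;
- ≥LLOQ.

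The table then matches the result categories in Protocol 8.2.9. The cost is one SAP sentence and one programming condition, with no new data. If the table is already built from laboratory result codes, only the sentence changes. The change concerns tabulation only and takes no position on any HBV management rule.

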- Endpoint: American College of Rheumatology (ACR) 20 at Week 12
- How to account for intercurrent events (ICEs): ICEs related to study intervention include the use of rescue or prohibited medication and early discontinuation (ED) from the study or study intervention. A composite strategy will be used for these types of ICEs. Specifically, participants with ICEs related to study intervention will be considered as treatment failure (having no change from baseline), that is, a nonresponder, after the first occurrence of these ICEs.
- Population-level summary: Difference in proportion of participants achieving response at Week 12 between each dosing regimen of peresolimab and placebo
- Rationale for estimand: The primary estimand strategy assumes that:

- o If a participant used any rescue or prohibited medication, the participant was not receiving sufficient benefits from study intervention.
- o If a participant early discontinued the study or study intervention, the participant experienced a burden of study intervention that outweighed its benefits.

Secondary estimand for categorical endpoints at Week 12

For secondary objectives that have categorical endpoints analyzed at Week 12, the clinical question of interest is:

What is the difference between peresolimab and placebo in the target patient population, in achieving a successful response at Week 12 without use of rescue or prohibited medications or discontinuing the study intervention?

The estimand is described by the following attributes:

- Population: Participants with moderately-to-severely active RA
- Endpoint(s): ACR50, ACR70, Disease Activity Score high-sensitivity C-reactive protein (DAS28-hsCRP) low disease activity (LDA), Disease Activity Score erythrocyte sedimentation rate (DAS28-ESR) LDA, Simplified Disease Activity Index (SDAI) LDA, Clinical Disease Activity Index (CDAI) LDA, DAS28-hsCRP remission, DAS28-ESR remission, SDAI remission, and CDAI remission at Week 12
- How to account for ICEs: ICEs will be accounted using the same estimand strategy as for the primary estimand.
- Population-level summary: Difference in proportion of participants achieving response at Week 12 between each dosing regimen of peresolimab and placebo
- Rationale for estimand: Refer to the rationale for the primary estimand.

Secondary estimand for continuous endpoints at Week 12

For secondary objectives that have continuous endpoints analyzed at Week 12, the clinical question of interest is:

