4.1. General Considerations

Statistical analysis of this study will be the responsibility of sponsor or its designee. A detailed SAP describing the statistical methodologies will be developed by the sponsor or its designee.

Handling of missing, unused, and spurious data are addressed prospectively in the overall statistical methods described in the protocol and in the SAP, where appropriate. Adjustments to the planned analyses are described in the final clinical study report (CSR).

Baseline for the Treatment Period is defined as the last nonmissing assessment on or prior to the date of the first injection of study treatment for efficacy, unless otherwise specified. In most cases, this will be the measure recorded at Week 0 (Visit 2). For safety analyses, baseline will be defined by period as last nonmissing assessment prior to the first dosing of each period. The Treatment Period starts after the first injection and ends on date of Visit 18 (Week 60) or early discontinuation (ED). Any assessment collected after the first injection is defined as postbaseline for the Treatment Period. If ET visit does not occur, last injection date will be considered as the end of the treatment period. Baseline for safety analysis of the Posttreatment Follow-Up period (Period 4) is defined as the last nonmissing assessment prior to entering Period 4, that is date of Visit 18 (Week 60) or ET.

During this study, data issue was identified for the collection date/time of the electronic clinical outcome assessments (eCOA). Same analysis visit was assigned to eCOA assessment with different collection date than the corresponding visit date. Because of this, study team came up with a method to handle this data issue, which is the analysis visit numbers for electronic clinical outcome assessments (eCOA) data will be assigned based on the actual visit date recorded in the electronic case report form (eCRF). If the eCOA assessment date is within +/- 3 days window of the actual visit, then the analysis visit number of the eCOA assessment will be assigned as the actual visit number. If the eCOA assessment date is outside +/- 3 days window of all the actual visits, then the analysis visit of the eCOA assessment will be considered as unscheduled visit. The eCOA data will be used for the analysis only when the analysis visit number of the eCOA assessment is identical to the visit number captured in the eCOA system.

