4.6.1. Extent of Exposure

Duration of exposure to study drug during the double-blind treatment period will be summarized by treatment arm and provided as listing. Duration of exposure on treatment will be calculated as the date of last dose of study drug (or date of discontinuation) minus the date of first dose of study drug plus 1 day. Total patient-years (PYs) of exposure will be reported for each treatment group for overall duration of exposure. Descriptive statistics (n, mean, SD, minimum, maximum, first quartile, median, third quartile, and maximum) will be provided for patient-days of exposure and the frequency of patient falling into different exposure ranges will be summarized. Exposure ranges are as follows:

- $>0, \ge 12$ weeks, ≥ 24 weeks, and ≥ 60 weeks
- >0 to <12 weeks, ≥12 weeks to <24 weeks, ≥24 weeks to <60 weeks, and ≥60 weeks

Overall exposure will be summarized in total PYs, which will be calculated as follows:

Exposure in patient years = $Sum \ of \ duration \ of \ exposure$ (for all patients in treatment arm) / 365.25.

No inferential analysis for comparison between treatment arms will be performed.

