4.6.2. Adverse Events

AEs are recorded in the eCRF. Each AE will be coded to System Organ Class (SOC) and Preferred Term (PT), using the *Medical Dictionary for Regulatory Activities* (MedDRA) version that is current at the time of database lock. Severity of AEs is recorded as mild, moderate, or severe.

A treatment-emergent adverse event (TEAE) is defined as an event that first occurred or worsened in severity after baseline and on or prior to the earliest of the visit study drug disposition dates or the last visit date during the treatment period, whichever occurred first, and up to 50 days after study treatment discontinuation. Baseline for Period 2 is defined as all preexisting conditions recorded at Visit 1 and any AEs recorded before the first dose of study intervention. Baselines for other periods are defined as unresolved AEs just prior to the first dose of each period. The MedDRA Lowest Level Term (LLT) will be used in defining which events

are treatment-emergent. The maximum severity for each LLT will be used as baseline. If an event is preexisting during the baseline period for Period 2, but it has missing severity, and the event persists during the treatment period or up to 50 days after treatment discontinuation, then the baseline severity will be considered mild for determining any postbaseline treatment-emergence (that is, the event is treatment-emergent unless the severity is coded mild at postbaseline). If an event occurring postbaseline has a missing severity rating, then the event is considered treatment-emergent. Should there be insufficient data for an AE start date to make this comparison (for example, the AE start year is the same as the treatment start year, but the AE start month and day are missing), the AE will be considered treatment-emergent. For events occurring on the day of the first dose of study treatment, Week 0 (V2) in most cases, the events will be assumed to occur posttreatment and considered as TEAE. For events occurring on the day of doses except for the first dose of study treatment, the events will be considered to occur prior to the study drug injection.

In general, summaries will include the number of patients in the safety population (N), frequency of patients experiencing the event (n), and relative frequency (that is, percentage; n/N*100).

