4.6.2.2. Allergic Reactions and Hypersensitivities

The current standard MedDRA Standardized Medical Queries (SMQs) to search for relevant events will be used. TEAEs are characterized as follows:

- Anaphylactic reaction SMQ (20000021)
- Hypersensitivity SMQ (20000214)
- Angioedema SMQ (20000024).

The frequency and percentage of patients experiencing treatment-emergent hypersensitivities will be summarized by treatment arm, SMQ, and PT during the Treatment Period. The frequency and percentage of patients experiencing treatment-emergent hypersensitivities will also be summarized by treatment arm and timing category.

Exposure-adjusted incidence rates (per 100 PYs) of treatment-emergent hypersensitivities will be summarized.

Total number of patients who experienced the TEAE for each PT while they were on Peresolimab will be divided by the sum of all patients' time (in 100 years) of Peresolimab

exposure during the treatment period. The entire time on the study during the Peresolimab treatment period will be used to calculate the patient's time of exposure.

The time to onset of first treatment-emergent hypersensitivity during the Treatment Period and the duration of each treatment-emergent hypersensitivity during the Treatment Period will also be defined and calculated in the same way.

A by-patient listing of all treatment-emergent hypersensitivities will be provided.

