If an AE has not ended by the date of completion or ED from the study, including the Posttreatment Follow-up Period, it will be censored as of that date. Descriptive statistics for the duration of treatment-emergent infectious AEs will be summarized by treatment arm. If a patient has more than 1 treatment-emergent infectious AE during the Treatment Period, then each AE will contribute to the analysis. If a patient does not have a treatment-emergent infectious AE during the Treatment Period, they will not be included in the analysis.

A by-patient listing of treatment-emergent infections will be provided.

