4.6.2.5. Malignancies

Malignancies will be defined using terms from the Malignant tumors SMQ (20000194) or Malignancies SMQ (20000090).

The frequency and percentage of patients with a treatment-emergent malignancy will be summarized by treatment arm, maximum severity, SOC, and PT during the Treatment Period. Exposure-adjusted incidence rates (per 100 PYs) for each type of treatment-emergent malignancy will be presented by treatment arm, and PT during the Treatment Period. AEs will be summarized under a particular time interval if they started or worsened on or after the interval start date and before the interval end date.

Malignancies excluding nonmelanoma skin cancers (NMSC) and NMSC will be also reported separately. NMSC will be defined using the below PTs:

- Squamous cell carcinoma of skin (10041834)
- Bowen's disease (10006059)
- Basal cell carcinoma (10004146)
- Basosquamous carcinoma (10004178)
- Basosquamous carcinoma of skin (10004179)
- Squamous cell carcinoma (10041823)
- Skin squamous cell carcinoma metastatic (10077314)
- Skin cancer (10040808)
- Carcinoma in situ of skin (10007390)
- Keratoacanthoma (10023347)
- Vulvar squamous cell hyperplasia (10079905)
- Skin squamous cell carcinoma recurrent (10081136)
- Lip squamous cell carcinoma (10064055)
- Penile Squamous cell carcinoma (10059631)

The time to onset of first treatment-emergent malignancies during the Treatment Period will be summarized in the same way as time to onset of first treatment-emergent infections.

A by-patient listing of treatment-emergent malignancies will be provided.

Additional information will be provided in the Adjudication Committee Charter.

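### Kaplan-Meier censoring for first infection and malignancy keeps participants who stop drug but stay in the study at risk after their events can no longer count

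*SAP*

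**What the plan says.** **Who is affected.** Protocol 7.1 encourages anyone who permanently stops study drug to remain for all remaining visits. Under the escape criteria (Protocol 7.1; SAP 1.2), persistent non-responders on rescue therapy should stop drug but may stay in the study.

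**When an event counts.** SAP 4.6.2 ends the treatment-emergent window at the earlier of the study drug disposition date and the last treatment-period visit, "whichever occurred first, and up to 50 days after study treatment discontinuation".

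**When time at risk ends.** For first treatment-emergent infection, SAP 4.6.2.4 says of participants without an event that "they will be censored at the date of completion or ED from the Treatment Period". Kaplan-Meier estimates are planned at Weeks 12, 24, 36, 48 and 60. For malignancy, SAP 4.6.2.5 says time to onset "will be summarized in the same way as time to onset of first treatment-emergent infections". SAP 4.1 ends the Treatment Period at Visit 18 (Week 60) or at ED. It adds that, if the early-termination visit does not take place, the last injection date is the end.

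**What ED means.** Protocol 7.2 ties the ED visit to leaving the study. The duration rule in SAP 4.6.2.4 begins: "If an AE has not ended by the date of completion or ED from the study". The estimand text in SAP 1.1 is wider: "early discontinuation (ED) from the study or study intervention".

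**Exposure-adjusted rates.** SAP 4.6.2.2 counts patients whose event occurred while on peresolimab and divides by peresolimab exposure during the treatment period. It then says: "The entire time on the study during the Peresolimab treatment period will be used to calculate" the patient's exposure time. SAP 4.6.1 defines exposure as "date of last dose of study drug (or date of discontinuation) minus the date of first dose of study drug", plus 1 day. The malignancy and depression rates (SAP 4.6.2.5 and 4.6.2.6) give no denominator of their own.

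**The concern.** A Kaplan-Meier risk set should hold only people who could still have a countable event. Someone who stops drug at Week 24 and attends to Week 60 can have no treatment-emergent infection after about Week 31. If censored at Week 60, that person counts as event-free for the rest of the curve whatever happens. The error runs in the reassuring direction and falls in the later part of the curve, where escape-driven stops accumulate.

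Infections and malignancy are both adverse events of special interest (SAP 4.6.2), and these curves are the planned long-term summary by arm. The exposure-adjusted rates raise the same question: a denominator that runs on to Week 60 for stayers includes person-time in which no event can enter the numerator.

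**Working it through.** The plan states no figure on this point, so there is none to reproduce. The check compares end dates and then sizes the effect.

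**Inputs from the documents:** 60-week Treatment Period; 50-day tail (50/7 = 7.14 weeks); about 60 participants on 100 mg and about 120 each on 400 mg and 1000 mg (SAP 5). A Week 24 stop is the example in Protocol 7.1. A Week 32 stop is the earliest under the SAP 1.2 wording, which needs failure at two consecutive visits after Week 24; it assumes equal 4-week spacing between Visit 9 (Week 24) and Visit 18 (Week 60).

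**Assumptions:** share of stayers f = 5–20%; 60-week incidence of first infection 40% (also 30% and 50%); constant hazard, unchanged by stopping; no other drop-out.

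**Step 1: end dates for one stayer**

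| | Stop Week 24 | Stop Week 32 |
|---|---|---|
| Window closes (stop + 7.14) | Week 31.14 | Week 39.14 |
| Weeks to Week 60 with no countable event | 28.86 (48.1% of 60) | 20.86 (34.8% of 60) |

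**Step 2: Week 60 curve.** λ = −ln(0.6)/60 = 0.00851 per week. With window end w, the planned curve shows

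S = (1 − f) × exp(−60λ) + f × exp(−λw), against a true value of exp(−60λ) = 0.600.

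- Stop Week 24: exp(−31.14λ) = 0.767. S = 0.95 × 0.600 + 0.05 × 0.767 = 0.608, or 0.80 × 0.600 + 0.20 × 0.767 = 0.633. Error 0.8 to 3.3 points. A simulation of 2 million participants at f = 20% gave incidence 36.7%, in agreement.
- Stop Week 32: exp(−39.14λ) = 0.717. S = 0.606 to 0.623. Error 0.6 to 2.3 points.
- With 30–50% incidence, the Week 24 case spans 0.7 to 4.0 points.

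**Step 3: earlier time points, 40% incidence.** For a Week 24 stop, the error is 0.2–0.6 points at Week 36 and 0.5–2.1 at Week 48. For a Week 32 stop, it is nil at Week 36, because the window is still open, and 0.3–1.0 at Week 48.

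**Step 4: rare events.** For malignancy, the planned risk is roughly the true risk × (1 − 0.481f) for a Week 24 stop, 2.4–9.6% too low in relative terms. At an assumed 1% incidence that is 0.02–0.10 points.

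**Step 5: sampling error.** √(0.4 × 0.6/60) = 6.3 points for 60 participants; √(0.4 × 0.6/120) = 4.5 points for 120.

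**Step 6: the other reading of ED.** If ED includes stopping drug, a stayer is censored at the stop and infections in the next 50 days fall outside the curve. Expected number among 60 participants, Week 24 stop: 60 × f × exp(−24λ) × (1 − exp(−7.14λ)) = 0.14 to 0.58 at 40% incidence, and 0.1 to 0.7 across 30–50%. Events and risk time then end together, so the curve is not biased low, but it omits events that SAP 4.6.2 calls treatment-emergent.

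**Step 7: exposure-adjusted rates.** If a stayer's denominator runs to Week 60 and the numerator is limited to time on drug, the empty share of planned person-time for a Week 24 stop is f × 36/60 = 3–12%. If the numerator has the 50-day tail, it is f × 28.86/60 = 2.4–9.6%.

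**The case against.** The strongest reply is that the bias depends on what ED means. If it includes stopping drug, as in SAP 1.1, events and risk time both end at the stop and the downward bias disappears. The visit schedule that might settle this is not in the public copy. That is fair, but the texts nearest the point favor leaving the study: Protocol 7.2, the duration rule in the same SAP section, and SAP 1.2, which pairs Week 60 with the Early Discontinuation Visit. Neither reading gives the 50-day window. The last-injection rule in SAP 4.1 is a third candidate date, though it may not be meant for stayers who reach Visit 18.

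On the rates, SAP 4.6.2.2 limits its numerator to time on peresolimab. If the peresolimab treatment period also means time on drug, as exposure does in SAP 4.6.1, numerator and denominator agree. This stands as a possible reading, so the plan can mismatch but need not.

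A reader might also infer more than the documents support:

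- **Infection rates are understated.** No exposure-adjusted rate is planned for infections; only the Kaplan-Meier curve is affected.
- **Doses are compared unfairly.** Escape follows non-response, so the share of stayers could differ by dose. The documents give no such shares, and Table KDAF.3.1 plans no between-treatment comparison over the Treatment Period.
- **Events are lost.** All adverse events are listed, serious ones are summarized through follow-up, and counts of treatment-emergent events do not change.

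**Conclusion.** The point holds for the Kaplan-Meier analyses of infection and malignancy. On the most natural reading, a stated rule keeps stayers at risk after their window has closed and overstates late event-free proportions. How early the error starts depends on the stop date: a Week 24 stop reaches the Week 36, 48 and 60 estimates, a Week 32 stop only the last two.

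The effect is modest: for infections at Week 60, about 0.8–3.3 points (Week 24 stop) or 0.6–2.3 (Week 32 stop) at 40% incidence. For malignancy it is negligible in absolute terms. These figures rest on an assumed share of stayers, incidence and constant hazard. They are below the standard error of an arm, but the error is systematic and larger samples would not remove it.

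For the hypersensitivity, malignancy and depression rates, the narrower conclusion is that the wording allows person-time in which no event counts. The Week 12 ACR20 analysis and the efficacy estimands are untouched. Priority is minor.

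**What to change.** - **SAP 4.6.2.4, carried to 4.6.2.5.** Replace the censoring rule: censor at the earliest of the Visit 18 (Week 60) date, the date of study discontinuation or last contact, or 50 days after study treatment discontinuation. Only treatment-emergent events up to that date count. State that this date, not the last-injection rule in SAP 4.1, applies to these analyses.
- **SAP 4.6.2.2.** Use the same end date on both sides of the rate. The numerator becomes treatment-emergent events from first peresolimab dose to that date, replacing the on-drug restriction; the denominator is time over the same span. Refer to it from 4.6.2.5 and 4.6.2.6, which define no denominator now.

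Two details need a sentence each. The Week 60 cap shortens the tail for anyone who stops after about Week 53 (60 − 7.14 = 52.9), which suits an analysis of the Treatment Period. For early leavers, say whether a post-treatment follow-up visit counts as last contact. Later events stay in the listings.

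The cost is a few lines of text and one derived date per participant, with no new data, visits or protocol amendment. SAP version 3 is already signed (01-Dec-2024), so this needs an addendum if the final database is not yet locked. The documents do not say whether it is. After lock, describe the change in the clinical study report.
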